#### 9.1.6 Documentation of Concomitant Medications

Concomitant medication is any drug given in addition to the study drug. These may be prescribed by a physician or obtained by the subject over the counter. Concomitant medication is not provided by Takeda. At each study visit, subjects will be asked whether they have taken any medication other than the study drug (used from signing of informed consent through the end of the study), and all medication including vitamin supplements, over-the-counter medications, and oral herbal preparations, must be recorded in the eCRF. Drugs given during the collection will be recorded as concomitant medication. Documentation will include generic medication name, dose, unit, frequency, route of administration, start and end dates, and reason for use.

#### 9.1.7 Documentation of Concurrent Medical Conditions

Concurrent medical conditions are those significant ongoing conditions or diseases that are present at signing of informed consent. This includes clinically significant laboratory, ECG, or physical examination abnormalities noted at Screening/Baseline examination. The condition (ie, diagnosis) should be described.

c) SRD/MRD heart rate will also be obtained on the days of dosing (Day 1 and Days 6-18) at 0.5, 1.5, and 2 hours postdose.

## 9.1.8 Procedures for Clinical Laboratory Samples

All samples will be collected in accordance with acceptable laboratory procedures. Laboratory samples will be taken following a minimum 10-hour overnight fast on the days stipulated in the Schedule of Study Procedures for SRD Part 1 (Appendix A and Appendix B) and SRD/MRD Part 2 (Appendix C).

Table 9.b lists the tests that will be obtained for each laboratory specimen.

**Table 9.b** Clinical Laboratory Tests

Hematology	Serum Chemistry	Urinalysis
Red blood cells (RBC)	ALT	pН
White blood cells (WBC)	Albumin	Specific gravity
with differential (absolute	Alkaline phosphatase	Protein
counts)	AST	Glucose
Hemoglobin	Total bilirubin	Blood
Hematocrit	Direct bilirubin	Nitrite
Platelets	Total protein	Leukocyte esterase
PT/INR	Creatinine	Ketones
aPTT	Blood urea nitrogen	Bilirubin
	Creatine kinase	Urobilinogen
	γ-Glutamyl transferase (GGT)	
	Potassium	
	Sodium	
	Glucose	
	Chloride	
	Bicarbonate	
	Calcium	

#### **Diagnostic Screening:**

Serum	Urine/Blood
HIV test	Drug screen including amphetamines, barbiturates,
Hepatitis panel, including HBsAg and anti-HCV	benzodiazepines, cannabinoids, cocaine, opiates, and
Female subjects: serum hCG (a)	cotinine. (c)
Female subjects, if menopause is suspected and not surgically sterile: FSH (b)	Female subjects: urine hCG (a).

aPTT=activated partial thromboplastin time, FSH=follicle-stimulating hormone, hCG=human chorionic gonadotropin. (a) Serum hCG pregnancy test will be done at Screening and Study Exit/Early termination, and at the Follow-up Visit if the subject is brought back to the clinic for re-evaluation. Urine hCG pregnancy test will be done at Check-in (Day -1).

The local laboratory will perform laboratory tests for hematology, serum chemistries, and urinalysis. The results of laboratory tests will be returned to the investigator, who is responsible for reviewing and filing these results. All laboratory safety data will be transferred electronically to Takeda or designee in the format requested by Takeda.

b) FSH level will be obtained for female subjects at Screening if they are postmenopausal (ie, no menses for 12 months without an alternative medical cause) and not surgically sterile. The result must be >40 IU/L for the subject to be enrolled.

c) To be performed at Screening and Check-in Day -1.

If subjects experience ALT or AST >3 × ULN, follow-up laboratory tests (at a minimum, serum alkaline phosphatase, ALT, AST, total bilirubin, GGT, and INR) should be performed within a maximum of 7 days and preferably within 48-72 hours after the abnormality was noted.

(Please refer to Section 7.5 for discontinuation criteria, and Section 10.2.3 for the appropriate guidance on Reporting of Abnormal Liver Function Tests in relation to ALT or AST  $>3 \times$  ULN in conjunction with total bilirubin  $>2 \times$  ULN.)

If the ALT or AST remains elevated >3 × ULN on these 2 consecutive occasions, the investigator must contact the Medical Monitor for consideration of additional testing, close monitoring, possible discontinuation of study drug, discussion of the relevant subject details and possible alternative etiologies. The abnormality should be recorded as an AE (please refer to Section 10.2.3 Reporting of Abnormal Liver Function Tests for reporting requirements).

The investigator or designee is responsible for transcribing or attaching laboratory results to the eCRF. The investigator will maintain a copy of the laboratory accreditation and the reference ranges for the laboratory used.

Laboratory reports must be signed and dated by the principal investigator or subinvestigator indicating that the report has been reviewed and any abnormalities have been assessed for clinical significance. Any abnormalities identified prior to first dose will require clear and complete documentation in the source documents as to the investigator's assessment of not clinically significant before proceeding with enrollment/randomization.

All clinically significant laboratory abnormalities must be recorded as a PTE/AE in the subject's source documents and on the appropriate eCRF. A clinically significant laboratory abnormality that has been verified by retesting will be followed until the abnormality returns to an acceptable level or a satisfactory explanation has been obtained.

#### 9.1.9 Telemetry

In the SRD Part 1, continuous cardiac monitoring (telemetry) will be performed from dosing on Day 1 through to approximately 36 hours postdose.

#### 9.1.10 Contraception and Pregnancy Avoidance Procedure

From signing of informed consent, throughout the duration of the study, and for 90 days after 5 half-lives have elapsed since the last dose of study drug (ie, 90 days from the Follow-up Call/Visit unless data indicates otherwise), nonsterilized\*\* male subjects who are sexually active with a female partner of childbearing potential\* must use barrier contraception (eg, condom with spermicidal cream or jelly). In addition, they must be advised not to donate sperm during this period.

From signing of informed consent, throughout the duration of the study, and for 30 days after 5 half-lives have elapsed since the last dose of study drug (ie, 30 days from the Follow-up Call/Visit unless data indicates otherwise), female subjects of childbearing potential\* who are sexually active with a nonsterilized male partner\*\* must use highly effective contraception (<1%)

failure rate/year), which has low user dependency. In addition they must be advised not to donate ova during this period.

\*Females NOT of childbearing potential are defined as those who have been surgically sterilized (hysterectomy, bilateral oophorectomy or tubal ligation) or who are postmenopausal (eg, defined as at least 1 year since last regular menses with an FSH >40 IU/L or at least 5 years since last regular menses, confirmed before any study drug is implemented).

\*\*Sterilized males should be at least 1 year postvasectomy and have confirmed that they have obtained documentation of the absence of sperm in the ejaculate.

A highly effective method of contraception for women of child bearing potential is defined as one that has no higher than a 1% failure rate per year. The acceptable methods of contraception are:

- Intrauterine device (IUD).
- Bilateral tubal occlusion.
- Vasectomized partner (provided that the partner is the sole sexual partner of the trial participant and that the absence of sperm in the ejaculate has been confirmed).
- Sexual abstinence if it is the preferred and usual lifestyle of the subject. Subjects practicing abstinence as a method of contraception must refrain from heterosexual intercourse throughout the duration of the study and for 30 days (females) or 90 days (males) after 5 half-lives have elapsed since the last dose of the study drug. This should be interpreted as 30 days (females) or 90 days (males) from the Follow-up Call/Visit unless available data indicates otherwise.

The use of hormonal contraceptives is not recommended for TAK-653 studies as there is currently no data on possible drug-drug interactions between TAK-653 and hormonal contraceptives.

Subjects will be provided with information on acceptable methods of contraception as part of the subject informed consent process and will be asked to sign a consent form stating that they understand the requirements for avoidance of pregnancy, donation of ova, and sperm donation during the course of the study.

Serum hCG pregnancy tests must be conducted for all female subjects at Screening and Study Exit/Early Termination. In addition to a negative serum hCG pregnancy test at Screening, subjects also must have a negative urine hCG pregnancy test prior to receiving any dose of study drug (eg, at Check-in Day -1).

During the course of the study, subjects will receive continued guidance with respect to the avoidance of pregnancy and sperm donation as part of the study procedures.

See Appendix A and Appendix B (SRD cohorts) and Appendix C (SRD/MRD cohorts) for the schedules for these procedures.

## 9.1.11 Pregnancy

If any subject is found to be pregnant during the study she should be withdrawn and any sponsor-supplied drug should be immediately discontinued. In addition, any pregnancies in the

partner of a male subject during the study or for 12 weeks after the last dose, should also be recorded following authorization from the subject's partner.

If the pregnancy occurs during administration of active study drug, eg, within 12 weeks of the last dose of active study drug, the pregnancy should be reported immediately, using a pregnancy notification form, to the contact listed in Section 1.0.

Should the pregnancy occur during or after administration of blinded drug, the investigator must inform the subject of their right to receive treatment information. If the subject chooses to receive unblinded treatment information, the individual blind should be broken by the investigator. Subjects randomized to placebo need not be followed.

If the female subject or female partner of a male subject agrees to the primary care physician being informed, the investigator should notify the primary care physician that the subject/male partner of the subject was participating in a clinical study at the time the woman became pregnant and provide details of treatment the subject received (blinded or unblinded, as applicable).

All reported pregnancies will be followed up to final outcome, using the pregnancy form. The outcome, including any premature termination, must be reported to the sponsor. An evaluation after the birth of the child will also be conducted.

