### 6.0 STUDY DESIGN AND DESCRIPTION

### 6.1 Study Design

This FIH, double-blind, placebo-controlled, combined SRD/MRD phase 1 study in healthy subjects is designed to assess the safety and tolerability of TAK-653. Approximately 112 healthy male and female volunteers will be enrolled.

This study consists of 2 parts: (1) single ascending doses in 5 cohorts (SRD) and (2) single and multiple ascending doses in 4 cohorts (SRD/MRD). Each cohort will consist of 8 subjects (6 active:2 placebo). Subjects will fast for at least 10 hours before dosing. Cohorts may be added or removed

This study will also provide a preliminary assessment of the potential effect of food on TAK-653 PK. Subjects in a selected SRD cohort (fasted conditions) will return to receive the same dose of TAK-653 under fed conditions after safety and tolerability has been established for TAK-653 at a higher dose under fasted conditions.

Follow-up assessments will occur approximately 14 days after the last dose of study drug to inquire for any ongoing AEs or serious adverse events (SAEs), worsening of AEs or SAEs, or development of new AEs or SAEs, and concomitant medications taken since final dose. Follow-up will occur by telephone unless abnormal, clinically significant findings are observed upon discharge or at the investigator's discretion. Subjects should then be brought back to the clinic for re-evaluation.

For all subjects in the SRD and SRD/MRD cohorts,

To assess change from baseline, the last assessment prior to the first dose of the study medication will be used.

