#### 7.1 Inclusion Criteria

Subject eligibility is determined according to the following criteria prior to entry into the study:

- 1. In the opinion of the investigator, the subject is capable of understanding and complying with protocol requirements.
- 2. The subject signs and dates a written, informed consent form and any required privacy authorization prior to the initiation of any study procedures including requesting that a subject fast for any laboratory evaluations.
- 3. The subject is a healthy adult male or female.
- 4. The subject is aged 18 to 55 years, inclusive at the time of consent.
- 5. The subject weighs at least 45 kg (99 lb) and has a body mass index (BMI) between 18.0 and 30.0 kg/m^2, inclusive at Screening.
- 6. A male subject who is nonsterilized\* and sexually active with a female partner of childbearing potential\* agrees to use adequate contraception\* from signing of informed consent throughout the duration of the study and for 90 days after 5 half-lives have elapsed since last dose of study drug. This should be interpreted as 90 days from the Follow-up Call/Visit unless data indicates otherwise.
- 7. A female subject of childbearing potential\* who is sexually active with a nonsterilized\* male partner agrees to routinely use highly effective contraception with low user dependency\* from signing of informed consent, throughout the duration of the study, and for 30 days after 5 half-lives have elapsed since the last dose of study drug. This should be interpreted as 30 days from the Follow-up Call/Visit unless data indicates otherwise.

\*Definitions and acceptable methods of contraception are defined in Section 9.1.10 Contraception and Pregnancy Avoidance Procedure and reporting responsibilities are defined in Section 9.1.11 Pregnancy.

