#### 7.4 Diet, Fluid, and Activity Control

Subjects will be confined to the clinic for the duration of each treatment period (see SRD Figure 6.a and SRD/MRD Figure 6.b).

During the confinement period, subjects will be given a menu for the dosing period that includes 3 meals and an evening snack, each containing approximately 30% fat (relative to the total calories). The meals served on the PK assessment days should be identical for each cohort in the study. The study menu should be recorded and submitted to the study file with a copy provided to

the sponsor prior to the start of the study. Record whether the meal was fully consumed, or, if not, record the percentage consumed (0, 25%, 50%, 75%).

If a blood draw or any study procedure coincides with a meal, the blood draw will take precedence followed by the study procedure and then the meal.

During the SRD Cohorts, except the fed portion of the food effect study, TAK-653 and placebo will be administered on Day 1 with 240 mL of water after a fast of at least 10 hours. Subjects will continue to fast for an additional 4 hours after dosing. Subjects may consume water ad libitum with the exception of 1 hour before and 1 hour after drug administration. Subjects do not have to fast on days when no dosing is scheduled.

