#### 9.3.6 Follow-up Call/Visit

Follow-up assessments are scheduled to occur on Day 14 (±2 days) for SRD subjects and Day 31 (±2 days) for SRD/MRD subjects to inquire for any ongoing AEs or SAEs, worsening of AEs or SAEs, or development of new AEs or SAEs, and for concomitant medications taken since final dose.

Subjects with unresolved SAEs, CS laboratory abnormalities, ECG or physical examination findings or at the investigator's discretion should return to the clinic for appropriate repeat procedure(s). A follow-up phone call will be made to all other subjects on Day 14 (±2) for an assessment of AEs and concomitant medications.

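### Partner pregnancies are recorded for 84 days after the last dose, but male contraception runs to about day 92-95 or day 103, so its last days need not be captured

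*Protocol*

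**What the plan says.** **Recording.** Protocol Section 9.1.11 covers pregnancies in the "partner of a male subject during the study or for 12 weeks after the last dose, should also be recorded", subject to the partner's authorization. A second sentence in that section deals with immediate notification. It also mentions 12 weeks, but as an example, and it is not confined to partners. The section then has all reported pregnancies followed to final outcome, with no time limit, apart from an exemption for subjects on placebo.

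**Contraception.** Inclusion criterion 6 binds nonsterilized men with a partner of childbearing potential "for 90 days after 5 half-lives have elapsed since last dose of study drug", and adds: "This should be interpreted as 90 days from the Follow-up Call/Visit unless data indicates otherwise". Section 9.1.10 repeats the rule, and exclusion criterion 9 applies the same period to sperm donation.

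**Timing.** Section 9.3.6: "Follow-up assessments are scheduled to occur on Day 14 (±2 days) for SRD subjects and Day 31 (±2 days) for SRD/MRD subjects". In Part 1 (Section 7.4), "TAK-653 and placebo will be administered on Day 1 with 240 mL of water"; in Part 2 (Section 6.1.2) the last dose is on Day 18.

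**The concern.** Two adjacent sections set different end dates for related obligations. The contraception rule defines how long the sponsor wants conception avoided after dosing; the pregnancy rule defines how long a failure of that precaution is recorded. If the second period ends first, a partner pregnancy that arises while the man is still bound by his eligibility commitment falls outside the recording duty.

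What is at stake is completeness of safety data in a first-in-human study. The toxicology studies listed in Section 4.1 are single-dose, escalating-dose, repeat-dose, genotoxicity and phototoxicity studies; no reproductive toxicity study is among them. Partner pregnancies will be few, so each one counts.

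**Working it through.** Neither the 12 weeks nor the 90 days is derived in the documents, so there is no calculation of the plan's own to reproduce. One stated figure can be checked. Section 6.1 says "Follow-up assessments will occur approximately 14 days after the last dose of study drug", and the visit days agree with it (step 2).

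**1. Recording limit.** 12 × 7 = 84 days after the last dose.

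**2. Follow-up relative to the last dose.** Follow-up day minus last dose day:
- Part 1: 14 − 1 = 13 days.
- Part 2: 31 − 18 = 13 days.
- With the ±2-day window: 11 to 15 days in both parts.

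**3. End of male contraception, operational reading** (90 days from Follow-up). 13 + 90 = 103 days after the last dose; range 11 + 90 = 101 to 15 + 90 = 105.

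**4. End of male contraception, literal reading** (90 days after 5 half-lives). Section 6.2.1 predicts a half-life of 10 hours from rat data and 26 hours from monkey data.
- 5 × 10 / 24 = 2.1 days, so the period ends at day 92.1.
- 5 × 26 / 24 = 5.4 days, so it ends at day 95.4.

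**5. Unrecorded tail** (contraception end minus 84).

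| Reading of the contraception rule | Ends, days after last dose | Tail, days |
|---|---|---|
| 90 days from Follow-up | 103 (101-105) | 19 (17-21) |
| 90 days after 5 half-lives, 10 h | 92.1 | 8.1 |
| 90 days after 5 half-lives, 26 h | 95.4 | 11.4 |
| 90 days alone (floor) | 90 | 6 |

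Recording stops first on every row.

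**6. Effect of the undefined study period.** Section 9.1.11 also records partner pregnancies during the study, without defining that term.
- If the study ends for each man at his own Follow-up (about day 13), the 84-day limit governs and the tail is as in the table.
- If it means the whole trial, which under Section 9.3.7 ends at the last follow-up of the last subject, a man whose last dose was D days before that date is covered to the later of day 84 and day D. On the operational reading the tail is then 103 − 84 = 19 days when D is 84 or less, shrinks as D goes from 84 to 103, and is nil from D = 103. The last-dosed men have D of about 13, so they keep the full tail.

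The documents give no calendar dates by cohort, so the number of men affected cannot be computed.

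**7. Female subjects.** Their contraception period ends 30 days from Follow-up: 13 + 30 = 43 days (41 to 45) after the last dose, inside 84. There is no gap.

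**8. Other provisions.** Routine adverse event collection ends 30 days after the last dose (Section 10.2.1.1). Section 10.2.2 sends later serious events to the sponsor if they are spontaneously reported and considered related to study participation. Sections 10.1.2 and 10.1.4 define events in the subject, not the partner. Neither provision clearly covers a partner pregnancy.

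**The case against.** The best case against the point is that it is small and that several stronger readings fail.

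- **Notification capped at 12 weeks.** A reader might infer that immediate notification also stops at 84 days. It does not: the 12 weeks there is an example. Only the recording sentence sets a limit.
- **Late pregnancies lost to follow-up.** A reader might infer that a pregnancy on day 95 would not be followed to outcome. The section follows all reported pregnancies without a time limit. The gap is in the duty to record, and nothing forbids recording a pregnancy that is volunteered later.
- **Nineteen days for every man.** The 103 days is derived, not stated, and rests on a practical stand-in for 5 half-lives that the protocol allows data to change. On the literal rule the tail is 8 to 11 days, and men dosed early may have none if the study period means the whole trial.
- **Little exposure by then.** At 26 hours, day 84 is 84 × 24 / 26 = 77.5 half-lives after the last dose, so the last days of the window are not equal in risk to the first.
- **Self-report throughout.** No contact is scheduled after Follow-up, so days 14 to 84 depend on the subject's report as much as the days after. What subjects are told cannot be judged, because the consent pages are not in the documents reviewed.

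All of this stands and limits the size of the point. None of it makes the recording period as long as the contraception period for men dosed late in the trial.

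**Conclusion.** The mismatch is real and minor. Partner-pregnancy recording ends 8 to 11 days before the male contraception period on the literal rule, and 17 to 21 days before it on the operational rule. This holds for all men if the study period is read subject by subject, and at least for late-dosed men if it is read as the whole trial.

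The figures assume that the predicted half-life of 10 to 26 hours applies to the literal rule, that visits fall within their windows, that no data have changed the contraception period, and that a pregnancy is dated by when it occurs rather than when it is detected. For the food-effect cohort they assume that Follow-up is counted from the second dose. The documents do not say which duration is intended, so the finding is an inconsistency to be reconciled, not an error in the contraception period itself.

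**What to change.** Reconcile Sections 9.1.10 and 9.1.11. In the sentence on partners of male subjects, replace the fixed 12 weeks with a cross-reference, so that recording runs at least to the end of the male contraception period set in Section 9.1.10. A cross-reference keeps the two aligned if emerging half-life data change that period. State also whether the study period there means the subject's own participation or the whole trial.

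Give the notification sentence a matching example for partners. Leave reporting for pregnant female subjects unchanged, and align any reporting instruction given to male subjects with the same end date.

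The cost is wording in one section and possibly in the subject information, plus a rare extra pregnancy report. The change touches data capture only; the contraception requirements and the statistical analysis stay as they are.
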